QDRS Total	0.3 (0.5)	3.5 (2.7)	7.2 (5.1)	11.7 (6.9)	11.6 (7.8)	7.4 (6.3)	<.001
QDRS Cognitive Subscale	0.2 (0.3)	1.5 (0.9)	3.1 (1.9)	4.5 (2.6)	2.8 (2.3)	2.7 (2.4)	.005
QDRS Behavior Subscale	0.2 (0.3)	2.0 (2.0)	4.2 (3.5)	7.5 (4.9)	8.8 (5.9)	5.4 (4.8)	<.001

Although initially tested as an informant rating, we examined the utility of the QDRS as a PRO tool. We compared informant QDRS, patient QDRS, and Gold Standard CDR and CDR-Sum of Box in 254 consecutive dyads presenting to neurology clinics. The QDRS ratings were not considered in the Gold Standard evaluation and were completed prior to the office visit by the informant and patients. Cronbach alpha was examined as a measure of internal consistency. The internal consistency of the two versions of the QDRS were: Informant QDRS: 0.939; Patient QDRS: 0.922, supporting that both versions have excellent psychometric properties. Intraclass correlation coefficients (ICC) were used to assess interscale reliability comparing CDR domains, Sum of Box, and global scores with the QDRS correcting for chance agreement. The ICC examines the proportion of responses in agreement in relation to the agreement expected by chance. An ICC between 0.55 and 0.75 is considered good agreement, whereas an ICC greater than 0.76 is considered excellent.

The informant and patient versions of the QDRS have high degrees of agreement, and both versions show good to excellent agreement with Gold Standard CDR (Table 5).

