**D.6. Integrating the PDM and QDRS within the Epic EHR:** We will leverage the processes and technologies currently and successfully in use every day in our clinical partner's primary care practices. These practices at both sites use Epic as their EHR and its related computerized decision support (CDS) engine and its patient-completed survey platforms. As indicated in the preliminary studies, EHRs contain detailed clinical data that can be accessed to run the PDM algorithm. EHRs also have a platform for patient reported outcome (PRO) survey in which we will integrate the QDRS for the selected primary care practices. The EHR-based CDS system will display the results of the screening to clinicians to promote the interpretation of the results by healthcare providers and patients. The Regenstrief Institute (see Resources section) has decades of experience in successful CDS research and implementation. Over the past three years, we have partnered with our Epic EHR clinical informatics colleagues to deploy various CDS tools such as patient reported surveys, predictive algorithms for social frailty, and deprescribing recommendations. These CDS tools provide clinicians with a graphical summary of the results with a focus on the factors driving these results. A similar approach will be adopted in this study, tailored through the extensive configuration options available in the Epic CDS engine. Patient registration at the primary care clinic would trigger the CDS process including patient completion of the QDRS. The CDS engine will also query the data sources for the required input features specific to the patient and invoke the PDM ML algorithm. Results will be displayed within the EHR user interface with an emphasis on the key features of the model that explain the final outcome for each individual patient, including actionable clinician-directed recommendations related to appropriate diagnostic work-up. The proposed workflow will be deployed in the two healthcare systems (Eskenazi Health and UHealth) and integrated within the flow of the primary care practices. We have received the approval from leadership at both sites for the deployment of both the PDM and the QDRS, as described in their letters of support. The technical infrastructure (including servers, EHR and CDS configuration options, and data connections) as well as the security and governance agreements already exist and therefore pose no threats to project objectives or risk of delayed timelines.

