Cognitive Status: The Montreal Cognitive Assessment will be used for a global screen. The rest of the cognitive battery includes the Uniform Data Set (UDS) battery used in the NIA Alzheimer Disease Centers: 15-item Multilingual Naming Test (naming); Animal naming and Letter fluency (verbal fluency); Craft Story for paragraph recall testing of episodic memory (craft story immediate and delayed recall). ; Number forward and backward and Trail making A and B (processing and visuospatial abilities). The Geriatric Depression Scale is performed for assessment of mood.

Informant-Based Rating Scales: The CDR^73 will be used for global staging, the Neuropsychiatric Inventory (NPI) to assess behavior, and FAQ to assess activities of daily living.

Determination of Cognitive Status: Global rating scales will be combined with cognitive performance, Clinician Assessed Medical Conditions, Clinician diagnosis and medical record review to assign individuals to the following diagnostic categories after a consensus conference: No Cognitive Impairment (NCI), Subjective Cognitive Impairment (SCI), Mild Cognitive Impairment (MCI) or ADRD. MCI categories will be attributed based on the number of cognitive domains affected (single vs multiple; amnestic vs non-amnestic). ADRD cases will be assigned etiologies (AD, LBD, VaD, FTD, or mixed).

Professional research assistants will undergo a detailed training by Drs. [name] and [name] and will be certified in conducting the UDS assessment. Similar to our previous process from various research studies, we will use several incentives to encourage patients who screened positive to undergo the diagnostic assessment. First, we will work with the patient's physician to recommend the assessment. Second, the study personnel will provide information on the importance of the assessment. Third, the assessment will be offered free of charge. If transportation is a barrier, the patient will be offered free transportation or home-based assessment. Fourth, patients and their care partners will be reimbursed for their time with a \$50 gift for each.

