For Secondary Hypothesis 2, the analyses will be the same as described for Hypothesis 1 of Aim 2, except that the outcome will be acceptance rates for recommended ADRD diagnostic work-up following positive screen. We hypothesize the acceptance rate will be 44% using AWV alone and 66% with the screening approach that combines AWV + PDM + QDRS.

Potential problems & alternative strategies: Same as those described for Aim 1 above.

**D.8.c. Sample Size & Power:** Calculations were performed with PASS, a comprehensive power and sample size software. All calculations assume two-sided tests and alpha = 0.05. For study 1 (i.e., Aim 1), a sample size of 15 cluster pairs consisting of 400 persons (26.667 persons per cluster) will provide 81% power to compare population values of 75% versus 85% in the outcome of % accuracy of classification. This is based on using nonlinear mixed models to compare two paired (i.e., dependent) proportions. The proportions are considered dependent instead of independent because all three screening approaches for study 1 will be performed in the same sample of 400. This approach was selected because it will increase power by allowing participants to serve as their own controls. Moreover, it is appropriate for a diagnostic validity study to compare methods in the same sample (i.e., method contamination is not an issue). This calculation assumes that participants are recruited from 15 clinics (i.e., clusters) and that the within-pair coefficient of variation (CV) between clusters is .058. The CV was calculated as  $CV = \text{SQRT} (ICC \times (1 - \phi) / \phi)$ , where the intraclass correlation coefficient (ICC) was assumed to be 0.01, and phi is 0.75 (i.e. the proportion of accuracy for one of the standard screening methods). The power will be slightly greater than 81% to detect values of 75% versus 85% in the AUC, based on power for comparing two dependent AUC's, assuming discrete cutoff values, and accounting for a sample inflation factor (IF), where  $IF = [1 + (M - 1) * ICC]$ , M = average number of persons per cluster, and the ICC is 0.01.

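### The Aim 1 reference diagnosis is not stated to be masked to PDM and QDRS results, so its independence from the tests is not assured

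*Combined protocol and SAP*

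**What the plan says.** **Reference standard.** D.7.a builds the Aim 1 diagnosis from global rating scales and cognitive performance, together with "Clinician diagnosis and medical record review to assign individuals to the following diagnostic categories after a consensus conference". It does not say whose clinician diagnosis counts, or whether that clinician has seen the screen.

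**Display of results.** D.6 describes the Epic decision support, which shows screening results to clinicians with the features that drive them and work-up recommendations: "Results will be displayed within the EHR user interface".

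**Timing.** D.10 and the timetable put deployment of both tools into Epic in Years 1 and 2, the period in which the 400 Aim 1 subjects are recruited and assessed. Section E places the assessment within 30 days of screening.

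**Use of screen status.** D.7.a plans incentives to "encourage patients who screened positive to undergo the diagnostic assessment", partly delivered by study personnel. D.7 and Section E say that every screened patient is assessed.

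**Masking.** None is stated for Aim 1. For the team's earlier study of informant and patient QDRS ratings, C.5 does state a safeguard: "The QDRS ratings were not considered in the Gold Standard evaluation".

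**The concern.** The diagnosis is a panel judgement. If the people who make it can see the screen result, or a clinician's opinion shaped by it, borderline cases may be settled in the direction of the screen. Agreement between test and reference then reflects partly the test itself. This is review bias, and it usually flatters the test.

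The reference label underlies every Aim 1 estimate: the AUCs set against 0.75 and 0.85, % accuracy, and the comparison of the combined approach with each tool alone. A label assigned with knowledge of the screen cannot be re-masked afterwards, so the safeguard has to be in place before the first consensus conference.

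**Working it through.** **1. The plan's own figure.** D.8.c gives 81% power for 75% versus 85% accuracy (paired), with 400 persons in 15 clusters (26.667 each), two-sided alpha 0.05, and "within-pair coefficient of variation (CV) between clusters is .058". The matched-pair cluster formula is

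power = Φ( √[(c − 2)d² / V] − 1.96 ), with V = (p₀q₀ + p₁q₁)/m + CV²(p₀² + p₁²).

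- V = (0.1875 + 0.1275)/26.667 + 0.058² × (0.5625 + 0.7225) = 0.01181 + 0.00432 = 0.01614
- √(13 × 0.01/0.01614) = 2.838, and Φ(2.838 − 1.96) = 0.810

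The 81% reproduces. It contains no term for the quality of the reference standard, so masking leaves it unchanged.

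**2. Is there a route to unmasking?** Set side by side, D.7.a (record review and an undefined clinician diagnosis), D.6 (results shown in the EHR), D.10 (deployment alongside recruitment) and D.7.a again (study personnel acting on a positive screen before the assessment) leave a route open. No sentence closes it.

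**3. Illustrative effect on AUC.** The documents give no Aim 1 prevalence and no degree of dependence, so both are assumptions here.

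- Model: scores are N(0,1) in non-cases and N(μ,1) in cases, with μ = √2 Φ⁻¹(true AUC). The screen is positive above μ/2. A share q of labels is replaced by the screen result. Prevalence is 10–30%, with 1,000,000 simulated subjects per setting.

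| q | True 0.75 appears as | True 0.85 appears as | True 0.75 if the same amount of label error is unrelated to the screen |
|---|---|---|---|
| 5% | 0.76–0.77 | about 0.86 | 0.72–0.74 |
| 10% | 0.78–0.79 | about 0.87 | 0.69–0.73 |
| 20% | 0.80–0.82 | 0.88–0.89 | 0.66–0.71 |

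In the 0.75 rows the labels actually changed are about 1.6%, 3.2% and 6.3% of all patients, because most replaced labels already agreed with the screen. The last column shows that ordinary reference error lowers AUC; only error that follows the screen raises it.

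For scale, the approximate standard error of an AUC of 0.75 with 400 persons is 0.032 (prevalence 30%) to 0.052 (10%), after applying the inflation factor 1 + (26.667 − 1) × 0.01 = 1.257 to the variance.

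**4. Illustrative effect on % accuracy.** If a share q of labels follows the screen, an accuracy of a becomes a + q(1 − a). From 75%, this gives 76.25%, 77.5% and 80% for q = 5%, 10% and 20%.

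**5. The comparison between tools.** Take two conditionally independent tools, each with sensitivity and specificity 0.75, and 52 cases in 400 (13%, assumed). The combined screen is positive if either tool is positive (D.8.a), so its sensitivity is 1 − 0.25² = 0.9375 and its specificity 0.75² = 0.5625. The mean of sensitivity and specificity is 0.75 for each tool and for the combination. Let q = 10%.

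- *Labels follow the either-positive flag.* Labelled cases are 52 − 0.325 + 15.225 = 66.9.
  - Combined: (63.975/66.9 + 196.075/333.1)/2 = 0.772
  - Single tool: (47.7/66.9 + 254.8/333.1)/2 = 0.739
- *Labels follow one tool only.* Labelled cases are 52 − 1.3 + 8.7 = 59.4.
  - That tool: (47.7/59.4 + 262.3/340.6)/2 = 0.787
  - Combined: (56.475/59.4 + 196.075/340.6)/2 = 0.763

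The first pattern favours the combination and the second works against it. The documents do not say which result, if any, the panel would see, so the direction is undetermined.

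**The case against.** A reader might infer that the reference diagnosis is contaminated and the AUC therefore inflated. The documents do not support that, for these reasons:

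- No section says that Aim 1 participants' results sit in the chart the panel reads. D.9 places Aim 2 go-live after the Aim 1 analysis, which points away from live display during Aim 1.
- D.7.a itemises the record review (comorbidities, medications, laboratory tests, imaging), and screen results are not on the list. Neither tool is named as an input to the diagnosis, so direct incorporation is not shown.
- The staff who encourage screen-positive patients are not said to be those who rate or vote. Subjects enter on the Table 6 criteria, not because they screened positive.
- Most of the reference standard is a separate assessment: neurological examination, MoCA, the UDS battery, CDR, NPI and FAQ. Table 6 also excludes prior ADRD or MCI diagnoses.

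All of this stands. It lowers the likelihood and probable size of any bias, but none of it is masking. The go-live statement in particular concerns Aim 2 and sets no rule for the Aim 1 panel.

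A second tempting reading sets the AUC shifts above against the 10-point difference the study is powered for. That mixes measures: the 81% concerns a paired difference in % accuracy between approaches, whereas the AUC table moves one tool on another scale. A bias shared by all approaches need not widen the gap between them.

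**Conclusion.** The concern holds as a gap in the safeguards. D.7.a does not mask the UDS assessors or the consensus panel, and the surrounding sections leave a route by which screen results could reach them. Independence of the reference standard is not assured, and AUC and % accuracy may be biased, probably upward. Neither the presence nor the size of a bias is established.

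Under the assumptions in the working, a true AUC of 0.75 would be overstated by about 0.01–0.02 if 5% of labels followed the screen and by about 0.05–0.07 if 20% did. The upper end matches or exceeds one standard error of the estimate, enough to matter against the 0.75 and 0.85 targets. The change is worth making because it is cheap now and impossible once labels are assigned.

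**What to change.** State in D.7.a that:

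- the UDS assessors and the consensus panel are masked to PDM and QDRS results;
- the record extract they receive leaves out PDM and QDRS displays and any later entry that cites them;
- staff who handle screen results or encourage screen-positive patients do not rate or vote on the same patients;
- the clinician diagnosis used by the panel is one made without the screen results, and by whom.

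Reconcile the statements in D.7 and Section E that all screened patients are assessed with the passage in D.7.a that encourages those who screened positive. When results are released to treating clinicians is for the sponsor to reconcile with these sections; no rule is proposed here.

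The cost is protocol wording, preparation of a filtered record packet, and allocation of existing staff so that the roles are separate. Sample size, alpha and the stated power are unaffected.

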beneficiaries with a low socioeconomic status (50%). The UHealth has primary care practices serving older adults residing in Miami-Dade, Broward, and Palm Beach Counties and serving underrepresented groups of African Americans (19%) and Hispanic (45%) populations throughout South Florida. Our interdisciplinary research team has long-standing relationships with many sites in the two states. In late 2019, we published the results of a randomized controlled trial evaluating the

benefits and harms of ADRD screening among 4,000 older adults attending rural, suburban, and urban primary care practices.

**D.3. Subjects Recruitment into the Clinical Validation (Stage III) Study:** To recruit patients from the above clinical setting into our clinical validation study and using similar processes to our previous studies, trained research assistants will work with the practice manager from each primary care practice to identify potential subjects who meet the inclusion and exclusion criteria outlined in the table below. The research assistants will make initial contact via a phone or face-to-face at the primary care practices to garner interest in participating in the study and verify if the patient meets the inclusion criteria (see Table 6). Based on the literature, our own pilot data, and our power analyses (described below), we anticipate approaching 1,000 eligible subjects to enroll and complete data on 400 subjects. Rolling enrollment will take place over 18 months with an average monthly enrollment of 23 subjects per month.

Table 6. Inclusion and exclusion criteria	
Inclusion criteria	Exclusion criteria
65 years or older	Prior ADRD or mild cognitive impairment diagnosis as determined by ICD-10 code
At least one visit to primary care practice within the past year	Evidence of any history of prescription for a cholinesterase inhibitors or memantine.
Ability to provide informed consent	Has serious mental illness such as bipolar or schizophrenia as determined by ICD-10 code
Ability to communicate in English or Spanish	Permanent resident of a nursing facility
Available EHR data from at least the past two or three years	

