
**D.7. Data Sources and Collection:** We will collect EHR data from all patients enrolled in the clinical validation study (identified data after obtaining informed consent from subjects) and from patients receiving care in all of the practices enrolled in the two pragmatic trials (de-identified data after obtaining consent from the practice leadership and receiving waiver from the IRB). For the clinical validation study, the research team will conduct a gold-standard ADRD assessment on all patients screened by the PDM and the QDRS.

**D.7.a. ADRD Diagnostic Assessment:** The ADRD assessment is modeled on the Uniform Data Set (UDS) 3.0 from the NIA Alzheimer's Disease Center program. The assessment will be performed face-to-face or via Zoom at research centers in Indianapolis and Miami. To accommodate subject preference, the assessment may be conducted at the subject's home for convenience. We have used such assessments for more than a decade with excellent quality assurance and completion. The ADRD assessment will include the following data that will be entered into a REDCap database, a browser-based, metadata-driven software and workflow methodology for designing clinical and translational research databases.

Subject interview and Medical Record Review will be used to collect information on demographics, primary language, alcohol/tobacco/substance use history, and family history. We will review the patient's medical records for the presence of comorbid conditions, medications, vitamin B12 level, thyroid test, syphilis tests, Complete Metabolic Panel (CPM) and brain imaging. When relevant to making a diagnosis and unavailable in the patient's record, laboratory tests or brain imaging – MRI, will be requested in collaboration with the primary care clinicians. Skilled nursing services will be utilized to perform blood draws with approximately 30ml of blood to be drawn from each patient, only one time.

Medical Evaluation: A detailed neurological examination will be completed by certified research staff. The Modified Hachinski Scale will assess vascular risks.

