Potential problems & alternative strategies: The distributional assumptions for the binary outcomes are minimal, which will decrease the need to consider alternative analytic methods and models. However, to ensure the analytic methods appropriately account for the clustering effect when estimating standard errors and p-values, we will perform bootstrap estimation (i.e., using 1,000 datasets resampled with replacement at the person level) of the standard errors and confidence intervals surrounding the estimated values for AUC and % accuracy, and the estimated values for the difference in these values between screening approaches. In addition, if missing data occur, we will impute data using the simulation-based “Multiple Imputation” method, in which multiple complete datasets with plausible values for missing data are generated using model-based prediction, and analytic results from imputed datasets are aggregated to calculate appropriate standard errors and p-values in the presence of imputed data. We will use 100 imputed datasets, even though 10 to 50 are considered sufficient. Inclusion of potential auxiliary variables in the imputation model will be considered. A sensitivity analysis will be performed using participants with complete data.

**D.8.b. Primary Aim 2:** Evaluate the practical utility and effect of the PDM, and the combined methods in improving the annual rate of new documented ADRD diagnosis in primary care practices.

For Primary Hypothesis 1, three pragmatic screening approaches (AWV alone, AWV + PDM, and AWV + PDM + QDRS) will be compared on the annual incidence rate of EHR documented ADRD using nonlinear mixed models to account for clinic-clustered data. In the two pragmatic trials, different patients are randomized (via their clinics) to each of the 3 arms, making the outcomes independent between the three screening approaches; however, data will still be correlated for Aim 2 due to clustering of patients within clinics, which will be handled by random effects in the mixed models. We hypothesize the incidence rate will be 6% using AWV alone and 13% with the screening approach that combines AWV + PDM + QDRS. Incidence rates for all arms, including for AWV + PDM, will be calculated along with their 95% confidence interval.

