## E. PROTECTION OF HUMAN SUBJECTS

### Risk to Subjects

Human subjects' involvement and characteristics: Our Digital Detection of Dementia (D) project include the execution of three complimentary studies; the Clinical Validation (stage III) Study and the two Pragmatic cluster-randomized controlled comparative effectiveness (phase IV) trials. These studies will include community-dwelling men and women aged 65 years and older, who receive primary care services within Eskenazi Health located in central Indiana and UHealth in south Florida. They will be English or Spanish speaking, have had at least one visit to primary care practice within past year with available electronic health record (EHR) data from at least three years. The aims of the first Clinical Validation (Stage III) study require a face-to-face or telephone interview and EHR review, to evaluate the accuracy of two scalable approaches for early detection of Alzheimer's disease and related dementias (ADRD); the Passive Digital Marker (PDM) and the Quick Dementia Rating Scale (QDRS). These approaches will be embedded within the EHR systems of diverse rural, suburban, and urban primary care practices in central Indiana and south Florida. Older adult patients represent a somewhat vulnerable group. Our research specifically targets this group in an attempt to enhance the current standard of early detection of ADRD and improve Health for these individuals.

Participants in the first Clinical Validation Study will be informed of the purpose of the overall all goal of Digital Detection of Dementia (D) project of using scalable screening approached to improve the early detection of ADRD in primary care practices) and the procedures related to the clinical Validation study. Signed informed consent will be obtained from these participants. For the clinical validation study, and once informed consent is given, the research team will conduct a gold-standard ADRD assessments (within 30 days of screening) on all patients screened by the PDM and the QDRS.

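### D.7.a aims the incentives for the gold-standard assessment at screen-positive patients although every screened validation participant must have it, which creates a risk of differential verification

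*Combined protocol and SAP*

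**What the plan says.** D.7 (Data Sources and Collection) states that, in the validation study, "the research team will conduct a gold-standard ADRD assessment on all patients screened by the PDM and the QDRS". Section E (Risk to Subjects) repeats this with a time limit: "gold-standard ADRD assessments (within 30 days of screening) on all patients screened by the PDM and the QDRS". The paragraph on sources of material in section E says the same a third time.

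D.7.a defines that assessment. Its last paragraph refers to the team's process in earlier studies and then says "we will use several incentives to encourage patients who screened positive to undergo the diagnostic assessment". Four measures follow. "First, we will work with the patient's physician to recommend the assessment". Study staff then explain why the assessment matters. "Third, the assessment will be offered free of charge", with free transport or a home-based assessment where transport is a barrier. Last, "patients and their care partners will be reimbursed for their time with a" 50-dollar gift each. Nothing in the documents extends this package to patients who screened negative.

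For missing data, D.8.a plans multiple imputation with 100 datasets and says that auxiliary variables will be considered. It adds: "A sensitivity analysis will be performed using participants with complete data". It does not mention a missing gold-standard diagnosis and does not list the variables in the imputation model. The monitoring table in section F covers completion of screening and of the diagnostic assessment, with no stated split by screen result.

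**The concern.** In an accuracy study, the chance of receiving the reference standard should not depend on the test result. If screen-positive patients are encouraged and screen-negative patients are not, more of the negatives may go unverified. Among verified patients, false negatives and true negatives are then under-represented, so sensitivity looks too high and specificity too low. Because most patients in primary care are free of ADRD, the loss of specificity dominates and percent accuracy falls. Percent accuracy is the outcome behind the Aim 1 power figure and carries the same 0.75 and 0.85 targets as the AUC.

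The text looks like a carry-over. C.3 describes an earlier trial in which patients were referred for a voluntary diagnostic assessment only if they screened positive, and D.7.a says it follows previous practice. Such wording suits a referral pathway but not a study in which everyone is to be verified. The carry-over is an inference; the conflict in the text is not.

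**Working it through.** **Which study the text governs.** D.7.b takes the pragmatic trials' outcomes from the EHR, and D.8.a takes the Aim 1 reference diagnosis from D.7.a. A free research assessment with gifts therefore belongs to the validation study.

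**The plan's own figure.** D.8.c gives 81% power for 75% versus 85% accuracy with 15 cluster pairs, 400 persons (m = 26.667), CV 0.058 and two-sided alpha 0.05. The matched-pair cluster formula is

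power = Φ( √{(c − 2)d² / [p₁(1 − p₁)/m + p₂(1 − p₂)/m + CV²(p₁² + p₂²)]} − 1.96 ).

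The bracket is 0.1875/26.667 + 0.1275/26.667 + 0.003364 × 1.285 = 0.01614. Then √(13 × 0.01/0.01614) − 1.96 = 0.88, and Φ(0.88) = 81%. The figure reproduces. It presumes 400 completers and says nothing about who they are.

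**Bias in a complete-case analysis.** Let v₊ and v₋ be the completion rates in screen-positive and screen-negative patients, and π the prevalence.

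- Se′ = Se·v₊ / [Se·v₊ + (1 − Se)·v₋]
- Sp′ = Sp·v₋ / [Sp·v₋ + (1 − Sp)·v₊]
- AUC for one cut-point = (Se′ + Sp′)/2
- Accuracy = [π·Se·v₊ + (1 − π)·Sp·v₋] / overall completion

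True Se = Sp = 0.75 matches the plan's 0.75 target for a single test. The completion rates and prevalences are assumptions; the documents give neither for this study.

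At 0.95/0.80: Se′ = 0.7125/(0.7125 + 0.2000) = 0.781 and Sp′ = 0.6000/(0.6000 + 0.2375) = 0.716.

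At 0.90/0.60: Se′ = 0.675/(0.675 + 0.150) = 0.818 and Sp′ = 0.450/(0.450 + 0.225) = 0.667.

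| v₊ / v₋ | Se′ | Sp′ | AUC | Accuracy at π = 6% / 13% / 30% |
|---|---|---|---|---|
| equal | 0.750 | 0.750 | 0.750 | 75% / 75% / 75% |
| 0.95 / 0.90 | 0.760 | 0.740 | 0.750 | 74.1% / 74.2% / 74.6% |
| 0.95 / 0.80 | 0.781 | 0.716 | 0.749 | 72.1% / 72.5% / 73.7% |
| 0.90 / 0.60 | 0.818 | 0.667 | 0.742 | 67.8% / 69.0% / 71.9% |

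**Combined rule.** A simulation used two markers (each with AUC 0.75, correlation 0 or 0.3, prevalence 13% or 30%, component specificity 0.75 or 0.90). Completion depended on the either-positive result, at 0.95/0.80 or 0.90/0.60. Component AUC moved by at most about 0.015, the binary combined AUC by about −0.03 to +0.015, and combined accuracy fell by about 1 to 7 points.

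**Comparison with planned enrolment.** D.3 expects 23 enrolments a month for 18 months: 23 × 18 = 414, against 400 with complete data. That is a loss of 14/414 = 3.4%, part of which may be rounding. Suppose all 14 were screen-negative. The negative fraction is 0.25π + 0.75(1 − π), or 0.72 to 0.60 for π of 6 to 30%. So v₋ = 1 − 0.0338/0.72 = 0.953 to 1 − 0.0338/0.60 = 0.944. With v₊ = 1, Se′ is about 0.76, Sp′ about 0.74 and AUC 0.750. By contrast, overall completion is 84 to 86% at 0.95/0.80 and 68 to 72% at 0.90/0.60. Those would need about 465 to 475 and 556 to 585 enrolled to yield 400.

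**The case against.** The strongest reply is that full verification is the plan. It is stated three times, once with a 30-day limit, and participants consent to the procedures before any baseline assessment. A reader might infer from D.7.a that verification bias is built into the design. The documents do not support that: bias arises only if screen-negative patients complete less often, and no completion rates by screen result are given. This part of the reply stands.

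A reader might also take D.3, "we anticipate approaching 1,000 eligible subjects to enroll and complete data on 400 subjects", as evidence of heavy non-completion. It is not. That drop includes refusal before consent and screening, which cannot depend on the screen result, and the planned enrolment of about 414 implies little loss afterwards. Nor is the 44% acceptance rate in D.8.b a forecast, since it concerns work-up after a positive screen in another setting.

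Other parts of the reply also stand. Zoom or home assessment is open on subject preference under D.7.a and section E, and the gift sentence does not itself repeat the screen-positive limit. The complete-case analysis is only a sensitivity analysis. Missingness that depends on the observed PDM and QDRS results is a case that multiple imputation can handle. AUC, on which the primary hypothesis rests, barely moves, and the fall in accuracy works against the hypothesised targets.

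The reply does not remove the conflict. The incentive list is introduced for screen-positives, so staff who follow it would treat the two groups differently. The imputation plan names neither the missing diagnosis nor the scores. If non-completers were replaced until 400 had complete data and then left out of the analysis, imputation could not correct the imbalance.

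**Conclusion.** The point holds as a conflict between D.7.a and the full-verification requirement in D.7 and section E, with a resulting risk of differential verification. It does not hold as a finding that the study is biased.

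The size is unknown. Under the assumed rates of 95%/80%, complete-case sensitivity rises by 3.1 points, specificity falls by 3.4 points and accuracy falls from 75% to about 72 to 74%, with AUC at 0.749. At 90%/60%, sensitivity rises by 6.8 points, specificity falls by 8.3 points and AUC falls by 0.008. If losses after enrolment are as small as D.3 implies, the shifts in sensitivity and specificity are about 1 point each. The main exposure is therefore percent accuracy and any reported sensitivity and specificity, in the complete-case analysis or in an imputation that omits the screen scores. The change is still worth making, because it is cheap now and unequal verification is hard to repair once data are collected.

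**What to change.** 1. Reword the incentive sentence in D.7.a so that the same incentives and contact effort go to every enrolled validation participant, whatever the PDM or QDRS result.
2. Report completion of the gold-standard assessment by PDM result and by QDRS result.
3. In D.8.a, state that a missing gold-standard diagnosis will be imputed with the PDM and QDRS scores in the model, and that screened participants without the assessment stay in the analysis rather than being replaced and dropped.

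The cost is a rewording in D.7.a, a reporting line, a short addition to D.8.a, and slightly more incentive and transport spending on screen-negative participants, whom the plan already commits to assess.
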